5.2.5 Hypersensitivity Reaction

Primary endpoints for hypersensitivity reaction are events meeting the criteria of an anaphylactic reaction and acute hypersensitivity reaction occurring within 2 hours of drug administration. As described in the case definition below, anaphylactic events include all terms listed in Category A, which consists of the narrow terms Type I hypersensitivity, anaphylactic shock and anaphylactoid reaction. In addition, combinations of the AE terms listed in Categories B, C and D will also be defined as anaphylactic events.

Category A: anaphylactic reaction, Type I hypersensitivity, anaphylactic shock, anaphylactoid reaction

Category B: dyspnoea, chest discomfort, cough, swollen tongue, oedema mouth, throat tightness, wheezing, laryngeal oedema, respiratory distress, sensation of foreign body, asthma, sneezing

Category C: swelling face, urticaria, pruritus, rash, eye swelling, pruritus generalized, rash, generalized, flushing, erythema, swelling, eye pruritus, lip swelling, rash pruritic, rash, erythematous, eyelid oedema, ocular hyperaemia, injection site urticaria, angioedema

Category D: hypotension, blood pressure decreased

To meet the definition of an anaphylactic event, a case has to meet one of the following criteria:

1. A narrow term or a term from Category A;
2. A term from Category B (Upper Airway/Respiratory) AND a term from Category C (Angioedema/Urticaria/Pruritus/Flush);
3. A term from Category D (Cardiovascular/Hypotension) AND either a term from Category B (Upper Airway/Respiratory) or a term from Category C (Angioedema/Urticaria/Pruritus/Flush)

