6.1.1 Primary Endpoints

The primary outcome of this observational study is malignancy. Additionally, the following safety events will be investigated:

- Autoimmune disorders
- Demyelinating disorders
- Serious infections or opportunistic infections
- Hypersensitivity reactions
- Other events:
 - congestive heart failure
 - aplastic anemia
 - serious bleeding events
 - serious skin reactions

MedDRA coding version 17.0 will be used to identify and define AEs of interest. The specific MedDRA codes used to determine AEs of interest will be provided in the SAP. Narrow scope SMQs and clinical validation of primary endpoints are provided in Section [5.2](#) of the protocol.

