3.2 General study level definitions

Any reference to comparator medication is referring to the 3 medication classes in the eligibility criteria (Corticosteroids, Immunosuppressants or treatment with biologics other than Cimzia) only.

[figure not shown]

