3.2.1.2 Person-time at risk calculations for acute events

Exposure person-time at risk will be calculated for each CD treatment using the following equation:

$$\text{Last Date} - \text{First Date} + 1$$

First date is defined as the latest enrollment date or first CD treatment date after enrollment (whichever is later) or the first dose of new treatment if switching treatments. Last date is defined as the earliest of the following:

- Date of safety event of interest (for incidence rate calculations only)
- Last dose date + treatment class-specific half-life exposure for product
- Date of discontinuation, withdrawal, or data cutoff

Any gaps in exposure, as illustrated in the figure below, will be included in the gap treatment group person-time at risk calculations for acute events. Any overlap in treatment groups will be included in the overlap group person-time at risk calculations for acute events.

Figure 2: Example person-time at risk for acute events

[figure not shown]

Figure 2 presents an example of a patient's exposure history. For this example, exposure person-time at risk would be calculated as follows:

Exposure person-time = (Last treatment date + Treatment class-specific half-life) – First treatment date + 1) + (earliest of End treatment date + treatment class-specific half-life exposure, last date in study, data cutoff date) – Resume treatment date + 1).

See Section 11.1, appendix 1 for more examples of treatment allocation scenarios for acute events.

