- Serious skin reactions (eg, Stevens-Johnson Syndrome, toxic epidermal necrosis, and erythema multiforme). These will be manually identified by the study physician from Serious TEAE table.

Although not officially AEs of interest, the following events will also be summarized as described in the AEs of Interest – Cimzia Program 2018-01-05 guidance document.

- Hepatic events. These will consist of a subset of all TEAEs, identified using the following 5 SMQs: Cholestasis and jaundice of hepatic origin; Hepatic failure, fibrosis, and cirrhosis and other liver damage-related conditions; Hepatitis, noninfectious; Liver-related investigations, signs and symptoms; and Liver-related coagulation and bleeding disturbances.
- Hypersensitivity reactions and anaphylactic reactions. Hypersensitivity reactions will be summarized as any TEAEs occurring on the same day or the day after injection was received, which code to the following preferred terms: Administration site hypersensitivity, Documented hypersensitivity to administered product, Drug hypersensitivity, Hypersensitivity, Hypersensitivity vasculitis, Infusion site hypersensitivity, Injection site hypersensitivity, Medical device site, hypersensitivity, Type II hypersensitivity or Type IV hypersensitivity reaction. Anaphylactic reactions will be defined using an algorithmic approach as described in the “AEs of Interest – Cimzia Program 2018-01-05” guidance document.
- Specific to study and not from the “AEs of Interest – Cimzia Program 2018-01-05” guidance document, we will also look at Malignant Lymphomas using the Narrow PTs from the “Malignant Lymphomas” SMQ, and into Autoimmune disorders and Lupus/Lupus-Like syndromes.
- Specific to study and not from the “AEs of Interest – Cimzia Program 2018-01-05” guidance document, we will also look at cases of non-melanoma Skin Cancer. These will be manually identified by the study physician from the TEAE table.

Table 8.1: Overview of malignancy events and acute events in this study

Overview of Events	
Event	Event Type (Malignancies are in addition analyzed following acute rules)
Malignant or unspecified tumor	Malignancy
Malignant tumor	Malignancy
Non melanoma skin cancer	Malignancy
Malignant Lymphoma	Malignancy
Serious infection	Acute
Opportunistic infection	Acute
Serious cardiac event	Acute
Congestive heart failure	Acute
Demyelinating-like disorder	Acute
Aplastic Anemia	Acute
Serious bleeding	Acute
Lupus and Lupus-like illness	Acute

Serious skin reaction	Acute

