Hepatic event	Acute
Hyper/Anaphylactic reaction	Acute
Autoimmune Disorder	Acute

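### The SAP counts a hypersensitivity event only around an injection, so comparator time without injections can add person-years but no events, and the Cimzia-to-comparator contrast can be inflated

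*SAP*

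**What the plan says.** **Protocol.** Section 5.2.5 defines the hypersensitivity endpoint as anaphylactic reaction and "acute hypersensitivity reaction occurring within 2 hours of drug administration". The trigger is any drug, by any route. Sections 3 and 5.2 name hypersensitivity among the adverse events of interest, and Section 6.1.1, under Primary Endpoints, lists "Hypersensitivity reactions" among the events to be investigated in addition to malignancy.

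**SAP definition.** Section 8.2.3 counts hypersensitivity as "any TEAEs occurring on the same day or the day after injection was received", limited to a list of preferred terms that includes "Documented hypersensitivity to administered product, Drug hypersensitivity, Hypersensitivity, Hypersensitivity vasculitis, Infusion site hypersensitivity, Injection site hypersensitivity". Anaphylaxis has its own rule: "Anaphylactic reactions will be defined using an algorithmic approach as described in the" sponsor guidance document, and the SAP text sets no injection window for it. Sections 2.2.1, 8 and 8.2.3 place both outside the official events of interest, yet Table 8.1 gives them one row, "Hyper/Anaphylactic reaction", analysed as an acute event.

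**SAP groups and denominator.** Section 3.2 limits comparator medication to three classes ("Corticosteroids, Immunosuppressants or treatment with biologics other than Cimzia) only"). Under Section 3.2.1.2, acute-event person-time for each treatment ends at the earliest of several dates, one being "Last dose date + treatment class-specific half-life exposure for product". Section 3.2.1.3 sets that extension at 7, 28 or 70 days by class. Section 3.6 splits acute events and person-time into Cimzia, Comparator, Overlap, Gap and Any Cimzia. Sections 8.1 and 8.1.5 plan to compare Cimzia rates with those of other Crohn's disease treatments and to give rate ratios.

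**The concern.** A rate comparison needs the same event to be countable in both denominators. Here the case definition depends on how the drug is given. A trigger written for an injected product is applied to a comparator that mixes three classes. Time on Cimzia together with a comparator goes to Overlap, so within Comparator time the qualifying injection has to be of a comparator product. Comparator time with no injected product contributes patient-years and, on the literal wording, no hypersensitivity events. That lowers the comparator rate whatever the true risk.

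Two further discrepancies need no assumption. The time window differs between the documents (two hours against same or next day), and so does the event's status. At stake is the reading of a safety event that the protocol names. A reader of the final report could take an effect of the case definition for an effect of the drug.

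**Working it through.** The documents give no hypersensitivity rate, ratio or power figure, so there is no planned figure to reproduce. Power is stated only for serious infections, lymphoma and solid malignancies.

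**Inputs.** The definition and the denominator rule come from SAP 8.2.3 and 3.2.1.2. All of the following are assumptions, because neither document gives them:
- s: share of Comparator person-time with no injected product.
- k: hypersensitivity rate in that time divided by the rate h in injected comparator time.
- q: share of anaphylaxis among comparator events in the pooled row if all were counted.
- fC, fI: share of events that the same-or-next-day window captures for Cimzia and for injected comparators.

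**Step 1: hypersensitivity alone, with fC = fI.**
- Comparator rate if all time could supply events: h[(1−s) + s×k].
- Comparator rate under the literal rule: h(1−s).
- Inflation of the Cimzia-to-comparator ratio: I = [(1−s) + s×k]/(1−s) = 1 + s×k/(1−s).

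| s | k = 0 | k = 0.25 | k = 1 |
|---|---|---|---|
| 0.2 | 1.00 | 1.06 | 1.25 |
| 0.5 | 1.00 | 1.25 | 2.00 |
| 0.8 | 1.00 | 2.00 | 5.00 |

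For example, s = 0.5 and k = 0.25 give 1 + 0.125/0.5 = 1.25. With equal capture, I is never below 1. It equals 1 when non-injected products cause no listed events.

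**Step 2: the pooled row.** Anaphylaxis is not restricted in the SAP text, so the row is inflated by 1/[(1−q)/I + q]. With I = 2:
- q = 0.10: 1/(0.45 + 0.10) = 1.82
- q = 0.25: 1/(0.375 + 0.25) = 1.60
- q = 0.50: 1/(0.25 + 0.50) = 1.33

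**Step 3: unequal capture.** The window also drops Cimzia events from the second day after injection onward. Measured against a definition with no window, the factor is (fC/fI)×I. The direction reverses if fC/fI is below 1/I, that is, below 0.50 when I = 2 or below 0.80 when I = 1.25.

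**Step 4: would an oral trigger repair it?** Suppose, for illustration only, a product given once every 28 days. A same-or-next-day window covers 2/28 = 7% of its days. For a drug taken daily the window covers 100%. Keeping the window and adding oral doses as a trigger would exchange one asymmetry for another.

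**The case against.** The strongest reply is that injection may be loose wording for administration. The same sentence lists an infusion-site term and an administration-site term as qualifying, and SAP 8.2.3 calls its descriptions brief and defers to a guidance document that is not available here. The intended rule may therefore already cover infused biologics. This stands as a caution. It does not remove the problem, since a programmer could implement the sentence either way, and time on products neither injected nor infused would still supply no events.

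A second reply concerns whether a ratio is planned at all. SAP 2.2.1 leaves hypersensitivity out of its list of events given rates and time-to-event statistics, and 8.1.3 promises hazard ratios for events of interest only. That is correct as far as it goes: a contrast is implied by Table 8.1 with Sections 3.6, 8.1 and 8.1.5, but it is not stated for this event. All analyses are descriptive, and malignancy is the primary outcome. Even so, rates shown side by side by treatment group will be compared.

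A reader might also infer that comparator patients can never meet the definition, so that the ratio is certainly inflated by 1/(1−s). The documents do not support this:
- They give no route for any comparator class.
- Other biologics can qualify, and so can a patient taking a non-injected drug together with an injected comparator.
- Anaphylaxis enters the row with no injection condition in the SAP text.
- 1/(1−s) is only the case k = 1, in which non-injected products cause listed events as often as injected ones.

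**Conclusion.** The mismatch between SAP 8.2.3 and Protocol 5.2 and 5.2.5 in trigger, window and status is plain from the text. The possible bias is conditional. If some comparator time is non-injected, if it gives rise to listed events, and if the window captures Cimzia and injected-comparator events equally, the hypersensitivity contrast is pushed upward by 1 + s×k/(1−s). At s = 0.5 this runs from 1.00 to 2.00 as k goes from 0 to 1, and a factor of 2.00 falls to 1.60 in the pooled row if anaphylaxis is a quarter of events. The actual size cannot be found from the documents. The SAP should be corrected, because its stated rule can distort the comparison for a safety event named in the protocol. The point does not touch the malignancy analysis.

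**What to change.** - Reconcile the trigger, the time window and the event-of-interest status with Protocol 5.2 and 5.2.5. Use one window and give the reason for it. The documents do not say whether clock times are recorded, which decides whether a two-hour window can be applied.
- Replace injection with administration of any injected or infused Crohn's disease product.
- For this event, compare Cimzia with injected or infused comparator products only, leaving person-time on other comparator products out of that denominator. Show the planned all-comparator rate beside it, labelled as not like-for-like.
- Report anaphylaxis separately from hypersensitivity.
- Do not add an oral trigger with a same-or-next-day window, because a daily drug would always be inside it.

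**Cost.** SAP wording, a restricted denominator for one event, and one extra table row. The comparator denominator for this event becomes smaller and its interval wider. Product or route must be identifiable from the exposure records. SAP 8.1.1 already tabulates biologics by name, but Protocol 4.8.2 gives dose and frequency as its examples of exposure detail and does not mention route. If route is missing for some products, state the classification rule used.

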5.2 Adverse Events of Interest

- Autoimmune disorders, such as:
 - systemic lupus erythematosus
 - rheumatoid arthritis
- Demyelinating disorders, such as:
 - multiple sclerosis
 - Guillain-Barre syndrome
 - chronic inflammatory demyelinating polyneuropathy
- Serious infections including opportunistic infections, such as:
 - tuberculosis
 - pneumonia
- Lymphoma and other malignancies, such as:

- hepatosplenic T-cell lymphoma
- non-Hodgkin's lymphoma
- solid malignancies
- Acute hypersensitivity reactions occurring within 2 hours of drug administration, such as:
 - urticaria, rash, pruritus, flushing, swollen lips/tongue/pharynx, wheezing, dyspnea, hypotonia, cramping, abdominal pain, and vomiting
- Other events:
 - congestive heart failure
 - aplastic anemia, pancytopenia, thrombocytopenia, neutropenia and leucopenia
 - serious bleeding events
 - serious skin reactions (eg, Stevens Johnson Syndrome, toxic epidermal necrosis, and erythema multiforme)

When available, narrow scope SMQs (Standardized MedDRA Queries) from the Medical Dictionary for Regulatory Activities (MedDRA®) version 17.0 will be used to define the AEs of interest (Section 5.2). Adverse events of interest that are the clinical endpoints for the SECURE registry will be confirmed by review of the results of diagnostic tests and diagnostic criteria used by the Investigator which are further explained within each section below.

Table 5–1: Standardized MedDRA Queries for select adverse events of interest

Event	SMQ Title	SMQ Code	SMQ Scope
Malignancy	Malignant tumours	20000194	Narrow PTs
Congestive Heart Failure	Cardiac failure	20000004	Narrow PTs
Serious skin reactions	Severe cutaneous adverse reactions	20000020	Selected Narrow PTs
Hypersensitivity reactions	Anaphylactic reaction	20000021	Narrow/Broad PTs
Serious bleeding events	Haemorrhage	20000038	Narrow PTs
Aplastic anemia	Haematopoietic cytopenias affecting more than one type of blood cell	20000028	Narrow PTs
Aplastic anemia	Haematopoietic erythropenia	20000029	Narrow PTs

Table 5–1: Standardized MedDRA Queries for select adverse events of interest

Event	SMQ Title	SMQ Code	SMQ Scope
Aplastic anemia	Haematopoietic leukopenia	20000030	Narrow PTs
Aplastic anemia	Haematopoietic thrombocytopenia	20000031	Narrow PTs

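### The SAP's ten hypersensitivity terms include none of the 11 reactions the protocol names, so an isolated acute urticaria or rash coded to its own term enters no hypersensitivity analysis.

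*SAP*

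**What the plan says.** Protocol 5.2 lists as AEs of interest "Acute hypersensitivity reactions occurring within 2 hours of drug administration, such as" and gives the examples "urticaria, rash, pruritus, flushing, swollen lips/tongue/pharynx, wheezing, dyspnea, hypotonia, cramping, abdominal pain, and vomiting". Protocol 5.2.5 then sets two components: "Primary endpoints for hypersensitivity reaction are events meeting the criteria of an anaphylactic reaction and acute hypersensitivity reaction occurring within 2 hours of drug administration". It writes out a term-based rule for anaphylaxis only. Apart from a narrow or Category A term, that rule needs a combination, for instance "A term from Category B (Upper Airway/Respiratory) AND a term from Category C (Angioedema/Urticaria/Pruritus/Flush)". Table 5–1 maps hypersensitivity to the Anaphylactic reaction SMQ with narrow and broad terms. Protocol 6.1.1 leaves the specific MedDRA codes to the SAP. Section 5 asks sites to enter AEs of interest whether or not they are serious.

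SAP 8.2.3 sets the time window for the hypersensitivity rule as follows: "Hypersensitivity reactions will be summarized as any TEAEs occurring on the same day or the day after injection was received". Inside that window it admits only a closed list of events, described as those "which code to the following preferred terms: Administration site hypersensitivity, Documented hypersensitivity to administered product, Drug hypersensitivity". The list goes on with one plain, unqualified hypersensitivity term and closes with these six: "Hypersensitivity vasculitis, Infusion site hypersensitivity, Injection site hypersensitivity, Medical device site, hypersensitivity, Type II hypersensitivity or Type IV hypersensitivity reaction". For the other component it says "Anaphylactic reactions will be defined using an algorithmic approach as described in the" sponsor's guidance document, which is outside the protocol and SAP. It describes both groups as not formally AEs of interest. Table 8.1 nevertheless carries a combined hypersensitivity/anaphylaxis category analysed under the acute-event rules.

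**The concern.** The protocol describes an acute hypersensitivity reaction by what the patient experienced. The SAP recognises it only by a diagnostic label. A site that writes 'drug hypersensitivity' contributes an event. A site that writes 'urticaria after injection' may not, although the protocol asked for both to be reported.

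The count for this category then reflects reporting style as well as risk, and any rate or time-to-event analysis run for it uses an incomplete numerator. If style differs between drugs or sites, the comparison could shift too. The point concerns which terms count. The different time windows (2 hours in the protocol, same or next day in the SAP) are a related mismatch.

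**Working it through.** There is no sample-size, power or alpha figure to reproduce. The check is a term-by-term comparison.

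**Inputs.** SAP list (8.2.3): 3 terms in the first part, 1 plain term and 6 in the last part, so 3 + 1 + 6 = 10, reading the medical-device entry as one term. Protocol list (5.2): 11 manifestations, or 13 if lips, tongue and pharynx are counted separately. Anaphylaxis rule (protocol 5.2.5): A, or (B and C), or (D and (B or C)).

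| Protocol manifestation | In SAP list? | Protocol 5.2.5 category | Alone meets the protocol's anaphylaxis rule? |
|---|---|---|---|
| Urticaria, rash, pruritus, flushing | No | C | No |
| Swollen lips/tongue/pharynx | No | lips C, tongue B, pharynx no exact term | No |
| Wheezing, dyspnea | No | B | No |
| Hypotonia, cramping, abdominal pain, vomiting | No | none (D holds only hypotension and decreased blood pressure) | No |

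**Result 1.** Overlap of the two lists: 0 of 11 (0 of 13 if split).

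**Result 2.** Under the protocol's rule, urticaria with wheezing (B and C) and rash with hypotension (D and C) qualify as anaphylaxis. Urticaria, rash, pruritus or flushing alone does not.

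**Result 3.** Where an isolated urticaria coded to its own term does appear: SAP 8.2.2 tabulates every investigator-reported AE by SOC, HLT and PT and lists all eCRF AEs, and SAP 8.2.4 adds it to the SAE tables if serious. The acute-event rules place it in a treatment period. For a biologic that period runs to 70 days after the last dose, so a reaction on the day of dosing and one weeks later share a row. Patient counts in separate PT rows also cannot be summed to patients with any acute reaction.

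**Size.** Let p be the share of acute reactions coded only to a manifestation. Ignoring small changes in person-time, recorded rate = (1 − p) × true rate, and recorded ratio = true ratio × (1 − p for Cimzia) / (1 − p for comparator). If the two shares are equal, the factor is 1 and only the absolute rates are too low. Neither document gives p for either group.

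**The case against.** Several objections have force.

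- A reader might infer that these events are counted nowhere. That is wrong: Result 3 shows they are tabulated and listed. What they miss is the hypersensitivity category.
- The SAP's anaphylaxis algorithm is in a document not available here. Exclusion from that branch is shown only under the protocol's rule.
- Manifestations are not coded terms. A site that recognised an allergic reaction may have recorded it under that name, and it would then code to a listed term. How often this happened is not visible.
- The protocol is itself unclear. It gives no preferred-term list for isolated acute reactions, and Table 5–1 points to the anaphylaxis SMQ. The documents therefore do not support saying that the SAP deleted a fully defined endpoint.
- Despite the wording in protocol 5.2.5, protocol 6.1.1 makes malignancy the primary outcome, and the SAP calls all analyses descriptive.
- Adding every single respiratory, skin, cardiovascular and abdominal term would harm specificity. Abdominal pain is an anticipated SAE in protocol 5.3 and an HBI item. Neither document shows an investigator flag for acute reactions or clock times. The study ended on 28 August 2020, and SAP Amendment 5 is dated 1 September 2020, so new fields cannot be collected.

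These points limit the claim and the remedy. They do not remove the mismatch: the protocol describes a component separate from anaphylaxis and leaves its codes to the SAP, and the SAP's list omits every example the protocol gives.

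**Conclusion.** The point holds in a limited form. The hypersensitivity definition in SAP 8.2.3 covers 0 of the 11 manifestations in protocol 5.2. An isolated acute urticaria, rash, pruritus or flushing coded to its own term enters no hypersensitivity analysis defined in the SAP and does not meet the protocol's anaphylaxis rule. It is visible only in general AE output that is not tied to time since dosing.

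A reader might go further and attach a percentage to the undercount, or conclude that the treatment comparison is biased. The documents support neither. Any percentage would only restate an assumed p, and bias in the ratio needs wording to differ by treatment, for which the documents give no evidence.

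The conclusion assumes that events are coded to the manifestation term and that the unseen algorithm does not capture isolated reactions in some other way. It concerns a named safety endpoint and leaves the malignancy outcome untouched, so the change should be made but the study does not depend on it.

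**What to change.** Reconcile SAP 8.2.3 with protocol 5.2, 5.2.5 and Table 5–1, and state the anaphylaxis algorithm in the SAP or attach it.

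Keep the ten-term row as it is. Add a separate row, 'other acute hypersensitivity', for events coded to the protocol-named manifestations, at least the Category C skin and angioedema terms, within the SAP's existing day-based window after administration. Before analysis, and blind to treatment where feasible, the study physician confirms that each event was reported as an acute reaction. Non-specific terms (abdominal pain, cramping, vomiting, dyspnea) count only when so confirmed. Run the incidence-rate and time-to-event analyses with and without the new row.

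The cost is SAP wording, a longer term list and some physician review of events already collected. The SAP already uses study-physician identification for heart failure, lupus-like illness and serious skin reactions. A few non-allergic symptoms may enter, and the separate row makes them visible.
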